## 1.2.3

To determine whether levofloxacin prophylaxis reduces the incidence of (a) fever with neutropenia; (b) severe infection; and (c) death from bacterial infection.

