#### 9.0 STATISTICAL CONSIDERATIONS

## 9.1 Statistical Design

This study is a randomized trial to investigate the effect of levofloxacin on preventing bacteremia in children being treated for AL or undergoing HSCT. Patients will be randomized between levofloxacin and no levofloxacin during 2 consecutive cycles of chemotherapy for AL or during 1 HSCT. Randomization will be stratified by 4 groups: 1) *de novo*, secondary or relapsed AML or acute leukemia of ambiguous lineage treated with standard AML therapy; 2) relapsed ALL; 3) autologous stem cell transplantation; 4) allogeneic stem cell transplantation. The study is designed to analyze AL and HSCT patients separately.

The primary aim is to determine the effect of levofloxacin on the incidence of bacteremia during the study timeframe of 2 cycles of chemotherapy or 1 transplant procedure among AL and HSCT subjects respectively. Besides assessing the safety of levofloxacin, especially on musculoskeletal disorders, other secondary aims are to determine the effect of levofloxacin on: total days of antibiotic administration, incidence of fever with neutropenia, incidence of severe infection, incidence of death from bacterial infection, incidence of CDAD, incidence of IFI, resistance patterns of bacterial isolates from sterile site cultures, evolution of antimicrobial resistance from stool or peri-rectal swab isolates of *E. coli, K. pneumoniae, P. aeruginosa* and S. *mitis* and presence of stool colonization by carbapenem-resistant Enterobacteriaceae.

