#### 9.3.1.2 Secondary Endpoints

Stool surveillance testing will investigate for the following resistance patterns among stool commensals at the start and end day of each treatment period: the susceptibility of *E. coli, K. pneumoniae*, and *P. aeruginosa* stool or peri-rectal swab isolates to cefepime, imipenem and levofloxacin; the susceptibility of *S. mitis* peri-rectal swab isolates to cefepime, levofloxacin and penicillin. Additionally, the presence of carbapenem-resistant Enterobacteriaceae will be screened from each enrolled patient's second collected stool or peri-rectal swab. The trajectory of the resistance patterns for the gastrointestinal isolates colonizing each patient will then be evaluated. Data regarding the resistance patterns of bacterial isolates from all sterile site cultures will be described. In interpreting antimicrobial sensitivity testing of both gastrointestinal organisms and organisms isolated from sterile sites, an intermediate result will be considered resistant for analytic purposes.

A secondary endpoint will be the duration of parenteral antibiotic administration during the study timeframe of 2 cycles of chemotherapy or 1 transplant procedure. Each day of parenteral administration will be collected irrespective of the indication or type of antibiotic given and the observation timeframe will be the same as that described for the primary endpoint. Other secondary endpoints include the incidence of febrile neutropenia, severe infection and death from bacterial infection. Severe bloodstream bacterial, fungal, and clinically documented infections and death from bacterial infection will consist of episodes of infection that are graded as CTCAE version 4 Grades 4 or 5 respectively. Secondary

endpoints on musculoskeletal adverse events and particularly tendinopathy (tendonitis and tendon rupture) will be collected. CDAD will be defined as a positive *C. difficile* toxin assay result and diarrhea, CTCAE version 4, Grade 2 and higher. Microbiologically-proven IFIs will be recorded.

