For the secondary endpoint on total number of days of antibiotic administration, considering a 2-sample t-test, with about 133 AL patients per arm we will have 90% power to detect a difference of 0.4 SD between the 2 arms in the mean of the number of days of parenteral antibiotic administration at 2-sided alpha of 0.05; with about 200 HSCT patients per arm we will have 85% power to detect a difference of 0.3 SD between the 2 arms in the mean number of days of parenteral antibiotic administration. For the secondary endpoints on the incidence of febrile neutropenia, severe infection, and death from bacteremia, the observed incidence rate will be compared between the 2 randomized arms. The power of such secondary analyses depends on the baseline incidence and the difference in incidence between the 2 arms. For these secondary analyses, if, for example, we consider possible baseline incidence values of 40%, 30%, 20%, 15%, 10%, or 5% in the control arm, in AL group (about 133 patients per arm) we will have a power of 95%, 84%, 63%, 49%, 34%, or 19%, respectively, to detect a levofloxacin treatment effect if levofloxacin leads to a relative reduction of 50% in the corresponding baseline incidence rate (i.e., rate with levofloxacin of 20%, 15%, 10%, 7.5%, 5%, or 2.5% respectively); for HSCT group (about 200 patients per arm), the corresponding power for a 50% relative reduction in these baseline incidence rates will be 99%, 95%, 80%, 66%, 48%, and 26% respectively. The test considered is a Chi-square test with 2-sided alpha of 0.05. It can be seen that the power for detecting a treatment difference in these secondary analyses might be limited if the baseline incidence is rare.

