For the secondary endpoints, the total number of days of parenteral antibiotic administration will be compared between the 2 arms using 2-sample t-test. Wilcoxon rank sum test will also be considered. We will also use linear regression models to estimate any treatment difference in total days of parenteral antibiotic administration and adjust for randomization stratification and potentially other patient or treatment characteristics. The incidence of febrile neutropenia, severe infection from bacteremia, fatal infections from bacteremia and musculoskeletal adverse events will be compared between the 2 randomized arms similarly as the analyses on bacteremia. For the analysis on the incidence of tendon rupture, we will also consider separating levofloxacin patients into those with/without concurrent steroid use and comparing them separately to control patients, or adjusting for concurrent steroid use as covariate in logistic regression models. The incidence of CDAD and proven or probable IFIs will also be compared between the 2 study arms in a similar manner. A patient with multiple documented episodes of CDAD or proven or probable IFI will only be counted once when calculating the binary incidence rates. For these secondary endpoints, appropriate regression models that combine AL and HSCT patients will be performed to evaluate the treatment effect with levofloxacin in the two patient groups; test for interaction between treatment and patient group will be performed to examine if the effect of levofloxacin on these secondary endpoints differs between the two patient groups.

Factors that can potentially confound the true association of the randomized exposure (levofloxacin) with the primary and two of the secondary outcome measures (1.2.1 and 1.2.2) will be compared across the two randomization arms to assure a balanced distribution. These include the use of antibiotic or ethanol as dwells or locks in central venous catheters (CVC) to reduce CVC infections and the use of chlorhexidine gluconate baths to reduce CVC infections. Analyses adjusting for these factors will be exploratory in nature.

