## 9.5.1.2 Secondary Aim

The secondary aim is to determine whether prophylactic levofloxacin versus no levofloxacin is associated with an increased risk for the development of bacteremia or sterile site infection from either Gram positive or Gram negative resistant organisms. The following resistance scenarios will be considered independently:

- 1a. Levofloxacin resistant Gram positive and Gram negative organisms
- 1b. Cefepime resistant Gram positive and Gram negative organisms
- 1c. Imipenem resistant Gram positive and Gram negative organisms
- 1d. Penicillin resistance for *S mitis* only

The secondary hypotheses for these secondary aims are that the use of levofloxacin prophylaxis is associated with an increased risk of infection with levofloxacin resistant Gram positive as well as Gram negative organisms. Additionally, exposure to levofloxacin prophylaxis results in an increased risk of infection with both Gram positive and Gram negative organisms resistant to cefepime and imipenem. Lastly, levofloxacin prophylaxis is associated with an increased risk of penicillin resistant *S mitis*.

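### The analysis plan in 9.3.3 restricts severe infection and infectious death to bacteremia, which is narrower than the secondary endpoints set in 1.2.3, 9.1 and 9.3.1.2

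*Combined protocol and SAP*

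**What the plan says.** All references are to the combined protocol and SAP.

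- **Objective 1.2.3** asks whether prophylaxis reduces, besides fever with neutropenia, "b) severe infection; and (c) death from bacterial infection".
- **Section 9.1** repeats these aims as "incidence of severe infection, incidence of death from bacterial infection".
- **Section 9.3.1.2** lists them again: "Other secondary endpoints include the incidence of febrile neutropenia, severe infection and death from bacterial infection". It then describes their content: "Severe bloodstream bacterial, fungal, and clinically documented infections and death from bacterial infection will consist of episodes of infection", graded 4 or 5 under CTCAE version 4.
- **Section 7.1.2.1** collects severe (Grade 4 and 5) infections: bacterial and fungal ones with microbiological documentation, and clinically documented ones. It sets no bloodstream limit.
- **Section 9.3.2**, on power for the secondary endpoints, refers to "severe infection, and death from bacteremia, the observed incidence rate will be compared between the 2 randomized arms".
- **Section 9.3.3**, which assigns the tests, compares "The incidence of febrile neutropenia, severe infection from bacteremia, fatal infections from bacteremia and musculoskeletal adverse events" in the same way as the primary endpoint.

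On invasive fungal infection (IFI), 9.3.3 states: "The incidence of CDAD and proven or probable IFIs will also be compared between the 2 study arms". The word *probable* occurs only in 9.3.3, twice. Section 7.1.2.4 limits IFI data to culture or pathologically documented cases.

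**The concern.** The section that tells the analyst what to compare does not use the endpoints that the objectives and the endpoint section define. Bacteremia is not a loose word in this plan. Section 9.3.1.1 gives it a definition, with a rule for common contaminants, and 9.5.1.2 separates it from other infection when it speaks of "increased risk for the development of bacteremia or sterile site infection".

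Three things are at stake.

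- Events that are collected and named as endpoints would be left out of the comparison meant for them.
- For severe infection, 9.3.2 and 9.3.3 give the analyst two different event sets, and nothing says which section prevails.
- The narrowed endpoints lose independent information. A patient with a severe or fatal infection from bacteremia in the observation period would ordinarily already count as a primary-endpoint event, so the two comparisons become near-subsets of the primary one.

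The trial is open-label, so a choice of event set that is left until the data are in is best avoided.

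**Working it through.** **1. The plan's own figures.** The only numbers tied to these endpoints are the powers in 9.3.2: two-sided chi-square test, alpha 0.05, 50% relative reduction, about 133 per arm (AL) and 200 per arm (HSCT). With p2 = p1/2 and pbar = (p1 + p2)/2,

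power = Phi{ [ (p1 - p2) - 1.96 * sqrt(2 * pbar * (1 - pbar)/n) ] / sqrt( [p1(1 - p1) + p2(1 - p2)]/n ) }.

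Example, AL, 30% against 15%: (0.15 - 1.96 * 0.0512)/0.0504 = 0.985, and Phi(0.985) = 0.838. The plan states 84%.

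| Control rate | AL stated | AL recomputed | HSCT stated | HSCT recomputed |
|---|---|---|---|---|
| 40% | 95 | 94.9 | 99 | 99.3 |
| 30% | 84 | 83.8 | 95 | 95.2 |
| 20% | 63 | 62.8 | 80 | 80.2 |
| 15% | 49 | 49.0 | 66 | 66.2 |
| 10% | 34 | 34.0 | 48 | 47.5 |
| 5% | 19 | 18.7 | 26 | 25.9 |

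All 12 reproduce. No figure is wrong; the issue is which events the rates refer to.

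**2. The sections side by side.**

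| Section | Role | Severe infection | Death |
|---|---|---|---|
| 1.2.3 | objective | unrestricted | bacterial infection |
| 9.1 | aims | unrestricted | bacterial infection |
| 9.3.1.2 | endpoints | listed unrestricted, then described with the bacterial part limited to the bloodstream, plus fungal and clinically documented | bacterial infection |
| 9.3.2 | power, comparison | unrestricted | bacteremia |
| 9.3.3 | analysis | bacteremia | bacteremia |

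Section 9.3.1.2 is mixed, so it cannot be counted as plainly unrestricted for severe infection.

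**3. Where each type of event falls.**

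- *Severe infection with bacteremia*: counted under every section.
- *Grade 4-5 clinically documented infection without bacteremia*: an endpoint under 1.2.3 and 9.3.1.2, recorded under 7.1.2.1, not compared under 9.3.3.
- *Grade 4-5 fungal infection without bacteremia*: the same for severe infection. If culture or pathologically documented, it still enters the separate IFI comparison in 9.3.3.
- *Grade 4-5 bacterial infection documented outside the blood*: recorded under 7.1.2.1 and within the plain wording of 1.2.3. It is not covered by the bloodstream wording of 9.3.1.2, and it is not compared under 9.3.3.
- *Death from bacterial infection without bacteremia*: an endpoint under 1.2.3, 9.1 and 9.3.1.2, but outside the wording of both 9.3.2 and 9.3.3.

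**4. Could the choice matter numerically?** The documents give no share of severe infections due to bacteremia, so this is an assumption with a range. Suppose severe infection occurs in 20% of controls, and 100, 75, 50 or 25% of it comes from bacteremia. The narrow endpoint then has a control rate of 20, 15, 10 or 5%. If the 50% relative reduction applies to both event sets, power is 63, 49, 34 or 19% (AL) and 80, 66, 48 or 26% (HSCT), which are the plan's own values. This is an illustration only.

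**5. IFI wording.** Sections 1.2.5 and 2.4 speak of microbiological documentation, 9.3.1.2 of microbiological proof, 7.1.2.4 of culture or pathology, and 9.3.3 of proven or probable cases. No section defines a probable case or plans a field for one.

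**The case against.** The best defence is that *from bacteremia* is shorthand. The paragraph in 9.3.3 opens by referring to the secondary endpoints, and 9.3.1.2 has just listed them, so a sensible analyst would return to that list. This is plausible, but it does not remove the conflict. Bacteremia has its own definition, 9.3.2 and 9.3.3 differ on severe infection, and both narrow death in the same direction. If shorthand was meant, the correction costs nothing in substance.

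Four parts of the defence stand, and each rules out a stronger reading that a reader might infer.

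- *That 9.3.3 removes all non-bloodstream bacterial infections from a clear definition.* Section 9.3.1.2 already limits the bacterial part of severe infection to the bloodstream. Against that section, the loss is the fungal and clinically documented parts, and the bacterial part is close to unchanged.
- *That fungal infections go unanalysed.* Culture or pathologically documented cases are compared separately as IFI.
- *That probable cases make the IFI endpoint uninterpretable or inflate it.* Section 7.1.2.4 restricts collection to culture or pathologically documented cases, so the stray term adds no planned events. The point is editorial.
- *That the narrowing costs a known amount of power.* The illustration assumes the same relative effect in both event sets. The documents do not support that assumption, and they give no share from which to calculate a loss.

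**Conclusion.** The mismatch is real and should be corrected. As written, 9.3.3 does not compare severe infection as the objective and 9.3.1.2 set it, and no section that assigns a comparison tests objective 1.2.3(c) as set. The affected events are Grade 4-5 fungal and clinically documented infections without bacteremia (for severe infection) and bacterial deaths without bacteremia (for death), in both the AL and HSCT groups.

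The number of such events cannot be derived from the documents and could be small. The conclusion rests on reading 9.3.3 literally and on the absence of any rule giving one section precedence. It does not reach the primary endpoint, the sample sizes or the stated powers, all of which are unaffected.

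**What to change.** 1. In 9.3.3, replace the two bacteremia-restricted items with severe infection and death from bacterial infection, as defined in 9.3.1.2.
2. In 9.3.2, change death from bacteremia to death from bacterial infection.
3. In 9.3.1.2, reconcile the bloodstream limit on severe bacterial infection with 7.1.2.1, which records such infections without a site limit. Without this step, item 1 would point to a definition that still leaves non-blood bacterial infections unsettled.
4. Editorial: delete *or probable* in both places in 9.3.3, and use the culture-or-pathology term of 7.1.2.4 for IFI throughout. This also settles whether a case documented only by pathology counts.

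Cost: no new data, because 7.1.2.1 and 7.1.2.4 already collect what is needed. The change is more than wording, since it alters which events are compared. Section 9.3.2 records that interim data on the HSCT control-arm bacteremia rate were released in fall 2013. The edit should therefore be a dated amendment, made without knowledge of these outcomes by arm.

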## 4.0 TREATMENT PLAN

## 4.1 **Overview of Treatment plan**

Timing of protocol therapy administration, response assessment studies, and surgical interventions are based on schedules derived from the experimental design or on established standards of care. Minor unavoidable departures (up to 72 hours) from protocol directed therapy and/or disease evaluations (and up to 1 week for surgery) for valid clinical, patient and family logistical, or facility, procedure and/or anesthesia scheduling issues are acceptable per COG administrative Policy 5.14 (except where explicitly prohibited within the protocol).

In this study, patients will be randomized to no levofloxacin (Arm A) or levofloxacin (Arm B) at time of enrollment. Patients in Arm A receive no protocol treatment. Patients in Arm B receive levofloxacin as detailed below.

The required observations and adverse event reporting are identical in the two arms. See Section 7 for required observations and Section 11 for Adverse Event reporting.

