## 7.1.2.1 General Infection Information

Data to be collected during the infection observation period will include incidence of fever with neutropenia, days of neutropenia, use of granulocyte-colony stimulating factor (G-CSF) and corticosteroid exposure (categorized as no exposure, ≤ 5 sequential days of or > 5 sequential days of corticosteroid treatment), incidence of signs or symptoms of tendinopathy (tendonitis or tendon rupture), incidence of fever, days until first fever, days of anti-fungal therapy given, hospitalization days, days of trial medication use, use of chlorhexidine baths (yes or no), use of prophylactic CVL locks (ethanol or antibiotic locks for bacteremia prophylaxis) (yes or no) and the name and start/stop dates for any oral and parenteral antibacterial therapy. Incidence of sepsis and severe bacterial and fungal microbiologically documented infections and clinically documented infections (CTCAE version 4, Grade 4 and Grade 5) will be recorded. For patients who die during the infection observation period and who have an autopsy performed, the report of the autopsy will be requested.

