## 9.3.4 Interim Monitoring

Interim efficacy monitoring on the incidence of bacteremia will be performed twice when data is available for approximately one-third and two-thirds of patients (separately for AL patients and HSCT patients). Monitoring boundary will be based on Lan-Demet's method with spending function  $\alpha t^2$ . Futility analyses based on conditional power will also be performed at the same time separately for each patient group. The probability of establishing efficacy of levofloxacin given the currently observed data will be calculated. In calculating the conditional power, the outcome for future patients will be assumed to follow the alternative hypothesis. If the conditional power falls below 10%, it will be considered evidence that it is unlikely to establish efficacy of levofloxacin in the particular patient group at the end of the study. The data will be referred to the COG Data Safety and Monitoring Committee (DSMC) for consideration of early termination for the particular patient group. Accrual will not be suspended for these interim monitoring and analyses. The incidence of musculoskeletal disorder will be monitored between the 2 arms by descriptive statistics and Fisher's exact test at each interim DSMC report, which occurs approximately every 6 months during the first 2 years and annually thereafter. For tendon rupture, as concurrent steroid use is considered a risk factor, the analysis will also be considered separately for levofloxacin patients with/without concurrent steroid use or with adjustment for steroid use. A previous report on > 2,500 patients found a small increase in the musculoskeletal disorder incidence (3.4% versus

1.8%) in levofloxacin treated patients; however our study is not powered to detect a difference of this magnitude. Therefore, the monitoring on incidence of musculoskeletal disorder will be informal and mainly for safety reassurance. Such safety monitoring will always be done at marginal alpha level of 0.05 and not adjusted for the multiple comparisons. If any such safety comparison suggests a significantly higher incidence of musculoskeletal disorder for levofloxacin, the study committee will carry out a review of the observed disorders; the results and any committee recommendation will be reported to the DSMC. The DSMC may also have its own assessment and recommendation about musculoskeletal event safety given the observed data.

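### One of the two optional steroid analyses for tendon rupture splits only the levofloxacin arm, so its contrasts mix steroid and drug effects

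*Combined protocol and SAP*

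**What the plan says.** Section 9.3.3 starts from an intact comparison: "musculoskeletal adverse events will be compared between the 2 randomized arms similarly as the analyses on bacteremia". For tendon rupture it then adds two options in one sentence, both worded as something the trial will consider. The first is "separating levofloxacin patients into those with/without concurrent steroid use and comparing them separately to control patients". The second, in the same sentence, is "or adjusting for concurrent steroid use as covariate in logistic regression models".

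Section 9.3.4 repeats the pair for interim safety monitoring of tendon rupture: "the analysis will also be considered separately for levofloxacin patients with/without concurrent steroid use or with adjustment for steroid use". It gives the reason: "as concurrent steroid use is considered a risk factor". Section 2.3 also lists corticosteroid co-administration among the main risk factors for tendon complications of quinolones.

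On data, Section 7.1.2.1 collects "corticosteroid exposure (categorized as no exposure", up to 5, or more than 5 sequential days) during the infection observation period. Section 4.1 states: "The required observations and adverse event reporting are identical in the two arms".

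**The concern.** The split is written for levofloxacin patients only. Read literally, a treated subgroup that is all steroid-exposed, or all unexposed, is compared with controls who are a mixture of both. If steroids raise the risk of rupture, the exposed subgroup will look worse than controls and the unexposed subgroup better, whatever the drug does. The first error could look like harm. The second is more awkward in an analysis meant to reassure, because it can hide real harm. Neither error is forced on the trial, since the same exposure data exist for controls.

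**Working it through.** The plan states no rate, power or sample size for this comparison, so there is no figure to reproduce.

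**Inputs from the documents**
- 333 patients per arm (Section 9.5.3.1) and 466 neutropenic episodes per arm (Section 9.5.3.2).
- Tendonitis and tendon rupture together at 0.5-0.6 cases per 100,000 treatments (Section 2.3). This is a general estimate and may not carry over to this population.
- Safety comparisons at an unadjusted alpha of 0.05; Fisher's exact test for musculoskeletal events (Section 9.3.4).

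**Assumed inputs (not in the documents)**
- Steroid prevalence q, equal in both arms: 30-70%.
- Steroid risk ratio R: 2-5.

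**Step 1: bias of the one-sided split.** Let r be the risk in unexposed controls and D the true drug risk ratio. The risk in all controls is r(qR + 1 - q). Then:
- exposed levofloxacin vs all controls: D x R / (qR + 1 - q)
- unexposed levofloxacin vs all controls: D / (qR + 1 - q)
- levofloxacin vs control within the same steroid category: D

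With D = 1, the extremes over the assumed range are:

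| Contrast | Lowest | Highest |
|---|---|---|
| Exposed vs all controls | q=0.7, R=2: 2/1.7 = 1.18 | q=0.3, R=5: 5/2.2 = 2.27 |
| Unexposed vs all controls | q=0.7, R=5: 1/3.8 = 0.26 | q=0.3, R=2: 1/1.3 = 0.77 |

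The correct value throughout is 1.00. Widening q to 25-75% gives 1.14-2.50 and 0.25-0.80.

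**Step 2: hidden harm.** With D = 2, q = 0.5 and R = 3, the denominator is 2. The exposed contrast gives 2 x 3 / 2 = 3.00 and the unexposed contrast gives 2 / 2 = 1.00. A doubling of risk disappears in the unexposed patients.

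**Step 3: does it matter for rupture?** Expected events per arm are 466 x 0.000005 = 0.0023 to 466 x 0.000006 = 0.0028, or about a 0.3% chance of even one. Suppose half the levofloxacin arm is exposed (166 patients), set against 333 controls with no events. Two ruptures give a Fisher p of (166 x 165)/(499 x 498) = 0.11. Three give (166 x 165 x 164)/(499 x 498 x 497) = 0.036. So at least three ruptures in the exposed subgroup are needed for p below 0.05. If the rate in unexposed patients is raised to an assumed 0.1%, with no drug effect, exact enumeration puts the chance of a false harm signal at about 0.8% for R = 3 and 2.3% for R = 5. Both are below the nominal one-directional 2.5%.

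**The case against.** The case against giving this weight is strong on scope. The split is something the trial would only consider, in addition to the randomized comparison. The same sentence offers covariate adjustment, which uses steroid data from both arms and addresses the confounding. Section 9.3.4 does not name the comparator at all, so the unsplit control group there is carried over from Section 9.3.3. The monitoring is described as informal; a significant excess of musculoskeletal disorder leads to committee review and a report to the DSMC, with no stopping rule attached. All of this stands and limits the point. It does not make the contrast valid. The plan gives no rule for choosing between the two options, and with almost no events the logistic model would probably not be estimable, which could leave the split as the workable choice.

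A reader might infer that the musculoskeletal safety aim rests on this contrast. It does not: musculoskeletal events are compared between the randomized arms in both sections.

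A reader might also carry the bias over to commoner musculoskeletal events. With an assumed 2% rate in unexposed patients, half exposed and R = 3, the exposed-versus-all-controls contrast is 6% vs 4%. Fisher's test would then falsely signal harm about 14% of the time with both cohorts pooled (166 vs 333), 8.1% in AL (66 vs 133) and 10.6% in HSCT (100 vs 200). The documents do not support using those figures here, because both sections confine the steroid split to tendon rupture.

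**Conclusion.** The one-sided split is an invalid contrast and should be replaced. Under the assumed 30-70% exposure and steroid risk ratio of 2-5, with no drug effect, it gives apparent risk ratios of 1.2-2.3 (exposed) and 0.26-0.77 (unexposed). The direction needs only that steroids raise the risk, which the plan accepts; the size rests on the two assumed inputs and on equal steroid use in the two arms.

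The fault is confined to one of two optional analyses of one rare outcome. It does not touch the randomized-arm comparison, the covariate-adjusted option, the primary endpoint or the sample size. At the cited event rate it would almost never change a conclusion. Low priority.

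**What to change.** In Sections 9.3.3 and 9.3.4, replace the one-sided split with a like-with-like comparison. Suggested text: *Tendon rupture will also be compared between levofloxacin and control within each corticosteroid category of Section 7.1.2.1, applied identically in both arms, and summarized by a stratified exact or Mantel-Haenszel estimate. If events are too few, counts will be reported by arm and steroid category.*

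Add two caveats. Steroid exposure is recorded after randomization, so the strata are supportive and not strictly randomized comparisons. The categories cover the infection observation period only, so for the 2- and 12-month assessments they describe earlier, not concurrent, exposure.

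The cost is one sentence in each section plus the caveats. The Section 7.1.2.1 categories are already required in both arms, so no new data collection is needed for a comparison on those categories.
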